#### STUDY AND SITE START AND CLOSURE

The Sponsor/designee reserves the right to close the study site or to terminate the study at any time for any reason at the sole discretion of the Sponsor. Study sites will be closed upon study completion. A study site is considered closed when all required documents and study supplies have been collected and a study-site closure visit has been performed.

The investigator may initiate study-site closure at any time, provided there is reasonable cause and sufficient notice is given in advance of the intended termination.

Reasons for the early closure of a study site by the Sponsor or investigator may include, but are not limited to:

- Failure of the investigator to comply with the protocol, the requirements of the IRB/IEC or local Health Authorities, the Sponsor's procedures, or GCP guidelines
- Inadequate recruitment of participants by the investigator
- Discontinuation of further study intervention development

If the study is prematurely terminated or suspended, the Sponsor shall promptly inform the investigators, the IECs/IRBs, the regulatory authorities, and any contract research organization(s) used in the study of the reason for termination or suspension, as specified by the applicable

Protocol Amendment No.: 05

regulatory requirements. The investigator shall promptly inform the participant and should assure appropriate participant therapy and/or follow-up.

#### **DISSEMINATION OF CLINICAL STUDY DATA**

In order to benefit potential study participants, patients, healthcare providers and researchers, and to help BMS honor its commitments to study participants, BMS will make information about clinical research studies and a summary of their results available to the public as per regulatory and BMS requirements. BMS will post study information on local, national or regional databases in compliance with national and international standards for disclosure. BMS may also voluntarily disclose information to applicable databases.

#### **CLINICAL STUDY REPORT**

A Signatory investigator must be selected to sign the clinical study report (CSR).

For each CSR related to this protocol, the following criteria will be used to select the Signatory Investigator:

- National coordinating investigator
- Participant recruitment (eg, among the top quartile of enrollers)
- Involvement in trial design
- Regional representation (eg, among top quartile of enrollers from a specified region or country)
- Other criteria (as determined by the study team)

#### SCIENTIFIC PUBLICATIONS

The data collected during this study are confidential and proprietary to sponsor or designee. Any publications or abstracts arising from this study must adhere to the publication requirements set forth in the clinical trial agreement (CTAg) governing [study site or investigator] participation in the study. These requirements include, but are not limited to, submitting proposed publications to sponsor or designee at the earliest practicable time prior to submission or presentation and otherwise within the time period set forth in the CTAg.

Scientific Publications (such as abstracts, congress podium presentations and posters, and manuscripts) of the study results will be a collaborative effort between the study Sponsor and the external authors. No public presentation or publication of any interim results may be made by any principal investigator, sub-investigator or any other member of the study staff without the prior written consent of the Sponsor.

Authorship of publications at BMS is aligned with the criteria of the International Committee of Medical Journal Editors (ICMJE, www.icmje.org). Authorship selection is based upon significant contributions to the study (ie, ICMJE criterion #1). Authors must meet all 4 ICMJE criteria for authorship:

Protocol Amendment No.: 05

1) Substantial intellectual contribution to the conception or design of the work; or the acquisition of data (ie, evaluable subjects with quality data), analysis, or interpretation of data for the work (eg, problem solving, advice, evaluation, insights and conclusion); AND

- 2) Drafting the work or revising it critically for important intellectual content; AND
- 3) Final approval of the version to be published; AND
- 4) Agreement to be accountable for all aspects of the work in ensuring that questions related to the accuracy or integrity of any part of the work are appropriately investigated and resolved.

Those who make the most significant contributions, as defined above, will be considered by BMS for authorship of the primary publication. Sub-investigators will generally not be considered for authorship in the primary publication. Geographic representation will also be considered.

Authors will be listed by order of significant contributions (highest to lowest), with the exception of the last author. Authors in first and last position have provided the most significant contributions to the work.

For secondary analyses and related publications, author list and author order may vary from primary to reflect additional contributions.

#### **APPENDIX 3**

ADVERSE EVENTS AND SERIOUS ADVERSE EVENTS: DEFINITIONS AND PROCEDURES FOR RECORDING, EVALUATING, FOLLOW-UP AND REPORTING

#### **ADVERSE EVENTS**

#### **Adverse Event Definition:**

An adverse event (AE) is defined as any new untoward medical occurrence or worsening of a pre-existing medical condition in a clinical investigation participant administered study treatment and that does not necessarily have a causal relationship with this treatment.

An AE can therefore be any unfavorable and unintended sign (such as an abnormal laboratory finding), symptom, or disease temporally associated with the use of study drug, whether or not considered related to the study drug.

## **Events Meeting the AE Definition**

- Any abnormal laboratory test results (hematology, clinical chemistry, or urinalysis) or results from other safety assessments (eg, ECGs, radiological scans, vital signs measurements), including those that worsen from baseline, considered clinically significant in the medical and scientific judgment of the investigator. Note that abnormal lab tests or other safety assessments should only be reported as AEs if the final diagnosis is not available. Once the final diagnosis is known, the reported term should be updated to be the diagnosis.
- Exacerbation of a chronic or intermittent preexisting condition including either an increase in frequency and/or intensity of the condition.
- New conditions detected or diagnosed after study intervention administration even though it may have been present before the start of the study.
- Signs, symptoms, or the clinical sequelae of a suspected drug-drug interaction.
- Signs, symptoms, or the clinical sequelae of a suspected overdose of either study intervention or a concomitant medication. Overdose, as a verbatim term (as reported by the investigator), should not be reported as an AE/SAE unless it is an intentional overdose taken with possible suicidal/self-harming intent. Such overdoses should be reported regardless of sequelae and should specify "intentional overdose" as the verbatim term.

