# 3.4.4.2 First-in-Human Study (Study IM027009)

The first-in-human (FIH) study for BMS-986278, Study IM027009, was a double-blind, placebo-controlled, randomized single-ascending-dose and multiple-ascending-dose study.

The primary objective of the study was to evaluate the safety and tolerability of single and multiple ascending oral doses of BMS-986278 in healthy participants. Secondary objectives included:

- To evaluate the plasma PK of single and multiple ascending oral doses of BMS-986278 in healthy participants.
- To evaluate the effect of a high-fat meal and of a modified gastric pH on the plasma PK of a single dose of BM-986278 in healthy participants.
- To compare the plasma PK of multiple ascending oral doses of BMS-986278 in Japanese and non-Japanese healthy participants.

Following both single and repeat administrations of BMS-986278, plasma concentrations of the parent compound peaked rapidly each day approximately 1.5 hours after dosing. A similar second peak, presumably due to enterohepatic recycling, was observed each day approximately 4.5 hours after dosing, followed by a log-linear decline. BMS-986278 area under the plasma concentration-time curve from time 0 extrapolated to infinite time (AUC[INF]) and Cmax increased proportionally with dose with both single and repeat administrations; oral clearance was independent of dose. Steady-state plasma concentrations of the compound were reached at approximately 6 days after the first administration of the compound. There was minimal plasma accumulation of BMS-986278 and its metabolites.

BMS-986278 was generally well tolerated at single doses up to 150 mg and at multiple doses of up to 125 mg BID for 14 days. No deaths or serious treatment-emergent adverse events (TEAEs) were reported, and no participant discontinued dosing due to TEAEs. There were no clinically significant laboratory findings. The maximum tolerated single dose was determined to be 150 mg. Dose-limiting toxicity was not observed up to 125 mg BID for 14 days.

BMS-986278 was associated with reversible, generally dose-dependent reductions in BP that generally reached a maximum 4 to 8 hours after dosing, returned to baseline within 24 hours, and were not associated with meaningful changes in HR. Orthostasis was infrequently observed in both placebo and active dose groups, with no clear association with BMS-986278. BP reductions were mostly asymptomatic.

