#### 9.2.5 AEs of Special Interest

AEs of special interest (AESIs) are AEs for a particular product or class of products that a Sponsor may wish to monitor carefully. AESIs may be serious or nonserious. Such events may require further investigation to better characterize and understand them. In the BMS-986278 clinical development program, certain *asymptomatic* and *symptomatic* BP-related AEs are defined as AESIs; however, there has been no definitive assessment on the causal relationship between these events and treatment with BMS-986278. Additional information about *asymptomatic* and *symptomatic* BP-related AEs will be collected on the case report form in order to better characterize and understand them.

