## Clinical Evaluation of Hypotension AESI

Includes any of the events meeting any of the asymptomatic or symptomatic low BP criteria.

Asymptomatic low BP criteria:

- Seated SBP < 85 mmHg (confirmed by retest within 15 minutes)
- Seated DBP < 55 mmHg (confirmed by retest within 15 minutes)
- Orthostatic hypotension (defined as a drop in SBP of  $\geq$  20 mmHg or DBP of  $\geq$  10 mmHg with assumption of an upright posture from either supine or seated to upright position) (confirmed by retest within 15 minutes)

Protocol Amendment No.: 05

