## 9.2.7 Laboratory Test Result Abnormalities

The following laboratory test result abnormalities should be captured on the AE eCRF page or SAE eCRF, as appropriate. Paper forms are only intended as a back-up option when the electronic system is not functioning.

- Any laboratory test result that is clinically significant or meets the definition of an AE or SAE
- Any laboratory test result abnormality that required the participant to have study treatment discontinued or interrupted
- Any laboratory test result abnormality that required the participant to receive specific corrective therapy

It is expected that wherever possible, the clinical rather than laboratory term would be used by the reporting investigator (eg, anemia versus low hemoglobin value).

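### Appendix 3 and Section 9.2.5 apply conflicting tests to a confirmed low-BP reading, so the hypotension AESI can be recorded differently between sites

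*Combined protocol and SAP*

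**What the plan says.** Section 9.2.5 treats AESIs as a kind of AE: they "are AEs for a particular product or class of products that a Sponsor may wish to monitor carefully". Under the hypotension AESI it states: "Includes any of the events meeting any of the asymptomatic or symptomatic low BP criteria". The asymptomatic criteria are seated SBP below 85 mmHg, seated DBP below 55 mmHg, or orthostatic hypotension, each confirmed by a retest within 15 minutes. The symptomatic criteria combine symptoms that the investigator thinks could stem from low BP with at least one BP or HR threshold. Neither set asks whether the finding is clinically significant. Section 5.1.2.1 uses the same criteria to trigger a withheld dose and extra monitoring. Sections 5.1.2.1 and 8.1 use them for reduction to 10 mg or discontinuation.

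Appendix 3, in its list of events that meet the AE definition, covers results of safety assessments and names vital signs. Such a result qualifies when it is "considered clinically significant in the medical and scientific judgment of the investigator". Abnormal findings of this kind "should only be reported as AEs if the final diagnosis is not available", and then: "Once the final diagnosis is known, the reported term should be updated to be the diagnosis".

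Section 10.4.3 tabulates AEs by system organ class and preferred term, summarises vital signs descriptively, and reports by arm the proportion who stop treatment because of BP changes. It names no AESI analysis and no count of participants who meet the low-BP criteria.

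**The concern.** Section 9.2.5 fixes the event by confirmed thresholds, and Appendix 3 puts an investigator's judgement in front of it. The events exposed to that judgement are the asymptomatic ones, where there is no complaint to prompt an AE entry.

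BP lowering is the safety signal that the protocol itself stresses. Section 3.4.4.2 reports generally dose-dependent reductions in the first-in-human study and adds: "BP reductions were mostly asymptomatic". Section 5.5 expects the two doses to reveal any difference in BP response. Section 10.1 makes PK and tolerability key factors in choosing a dose and does not expect 30 mg and 60 mg to separate on FVC. A low-BP count that depends partly on site habit is a weak basis for that choice.

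Laboratory findings are treated differently. Section 9.2.7 sends to the AE page "Any laboratory test result abnormality that required the participant to have study treatment discontinued or interrupted". There is no matching rule for BP, although meeting the BP criteria leads to a withheld dose.

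**Working it through.** The point turns on wording, and the plan has no figure of its own to reproduce.

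**One reading under both rules.** Take a confirmed seated SBP of 84 mmHg without symptoms.

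- *Judged clinically significant, no diagnosis.* AESI under Section 9.2.5 and AE under Appendix 3. The rules agree.
- *Judged not clinically significant.* AESI under Section 9.2.5, because 84 is below 85 and the reading is confirmed. It fails the Appendix 3 condition for vital-sign results. Since AESIs are AEs, both rules cannot be followed.
- *Cause identified at once.* Still an AESI under Section 9.2.5. Under Appendix 3 the diagnosis is reported in place of the finding. Section 5.1.2.1 expects some low BP to have an identifiable cause.
- *Cause identified later.* The event stays in the database, but its term becomes the diagnosis.

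**Is there a tie-breaker?** Section 9.2.5 collects extra case report form detail, but on BP-related AEs, which leaves open whether the reading was entered as an AE at all. Section 9.2.9 asks for significant worsening to be recorded, which brings judgement back. Section 5.1.2.1 requires dose reductions to be noted in the case report form, but does not require the reading behind them to be an AE. None of these says which rule prevails.

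**What the arithmetic can show.** Let *a* be the share of criterion events that are asymptomatic and *f* the share of those entered as AEs, with every symptomatic event entered. The share of the AESI captured in AE data is

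c = (1 − a) + a × f.

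The documents give neither *a* nor *f*. On assumed values:

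- a = 0.60: c = 100% at f = 1; 0.40 + 0.30 = 70% at f = 0.5; 40% at f = 0.
- a = 0.75: c = 100%; 0.25 + 0.375 = 62.5%; 25%.
- a = 0.90: c = 100%; 0.10 + 0.45 = 55%; 10%.

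The range runs from no loss (f = 1, Section 9.2.5 governs and is followed) to loss of all asymptomatic events (f = 0, which no text states).

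**Effect on the comparison of arms.** If c is equal in all arms, the absolute difference is multiplied by c and the risk ratio does not move. With assumed true incidences of 15% and 5%, the difference is 10 points and the ratio 15/5 = 3.0. At c = 0.70 these become 10.5% and 3.5%, a difference of 7.0 points and a ratio of 3.0. At c = 0.55 they become 8.25% and 2.75%, a difference of 5.5 points and a ratio of 3.0. These figures show the mechanism and are not estimates for this trial.

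**The case against.** The strongest reply is that Section 9.2.5 is the trial-specific rule and governs over a generic appendix. Appendix 3 does not call its list exhaustive. Its general definition says: "An AE can therefore be any unfavorable and unintended sign". Its list of events that are not AEs does not mention asymptomatic vital-sign findings. This is a fair reading, and under it nothing is lost. But the protocol does not state it, and for a vital-sign result the clinical-significance condition is the more specific part of Appendix 3. Sites could reasonably differ, so the conflict stands.

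The reply does defeat several stronger inferences that a reader might draw:

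- *The AESI loses its asymptomatic events.* It can lose some. Actual loss needs Appendix 3 to prevail and sites to leave readings out.
- *The diagnosis rule deletes events.* It renames them, possibly to a diagnosis of hypotension. Renaming affects the count only if AESIs are retrieved by preferred term, and the retrieval method is not specified.
- *The protocol says that asymptomatic events are the commonest in this trial.* The statement concerns BP reductions in healthy participants in the first-in-human study, not crossings of these thresholds in IPF or PF-ILD.
- *The events go unreported.* Orthostatic BP and HR are measured at every visit, dose reductions and reasons for discontinuation are recorded, and Section 10.4.3 summarises vital signs and BP-related discontinuations.

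It is also fair to say that Section 10.4 is a summary that defers detail to the SAP, and the documents hold no separate SAP text. The missing AESI table is therefore a gap still open to be filled, not proof that none is planned.

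**Conclusion.** The two passages conflict and must be reconciled. The same confirmed asymptomatic reading can be an AESI under Section 9.2.5 and not an AE under Appendix 3. Recording can therefore vary between sites, and the AESI can be under-counted in AE tables.

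The size is unknown. It depends on the asymptomatic share, on how often investigators judge such readings not significant, and on which rule sites follow. The documents inform none of these. A claim that recorded incidence is too low in every arm, or that the active-placebo difference is shrunk by a stated amount, would go beyond the text.

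The matter is still worth settling. It concerns a safety signal relevant to dose choice, and an objective count can be made from measurements that the protocol already requires.

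**What to change.** 1. **Reconcile the text.** State in Appendix 3 or Section 9.2.5 that a confirmed reading meeting any low-BP criterion of Section 5.1.2.1 is recorded as the hypotension AESI whatever the judgement of clinical significance, with any identified cause recorded as well.

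2. **Define the count.** In Section 10.4.3 or the SAP, derive from the recorded BP and HR data, including the confirmatory retests, the number and proportion of participants in each arm with at least one criterion event. Show asymptomatic and symptomatic events separately. The symptomatic criteria also need the recorded symptoms and the investigator's view that they could be due to low BP.

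The second step does not depend on AE entry, so it also covers readings taken before the wording is changed.

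The cost is one sentence of text and one programmed table. The downsides are more AE entries, a higher reported hypotension rate, and the need to confirm that retest values are in the database. No change to dosing or clinical management is proposed.

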## **Events NOT Meeting the AE Definition**

- Medical or surgical procedure (eg, endoscopy, appendectomy); the condition that leads to the procedure is the AE.
- Situations in which an untoward medical occurrence did not occur (social and/or convenience admission to a hospital).

#### **DEFINITION OF SAE**

If an event is not an AE per definition above, then it cannot be an SAE even if serious conditions are met.

Protocol Amendment No.: 05

#### **SERIOUS ADVERSE EVENTS**

## A serious adverse event (SAE) is defined as any untoward medical occurrence that, at any dose:

#### Results in death

Is life-threatening (defined as an event in which the participant was at risk of death at the time of the event; it does not refer to an event which hypothetically might have caused death if it were more severe)

Requires inpatient hospitalization or causes prolongation of existing hospitalization (see NOTE below)

#### NOTE:

The following hospitalizations are not considered SAEs in BMS clinical studies:

- A visit to the emergency room or other hospital department < 24 hours that does not result in admission (unless considered an important medical or life-threatening event)
- Elective surgery, planned prior to signing consent
- Admissions as per protocol for a planned medical/surgical procedure
- Routine health assessment requiring admission for baseline/trending of health status (eg, routine colonoscopy)
- Medical/surgical admission other than to remedy ill health and planned prior to entry into the study. Appropriate documentation is required in these cases
- Admission encountered for another life circumstance that carries no bearing on health status and requires no medical/surgical intervention (eg, lack of housing, economic inadequacy, caregiver respite, family circumstances, administrative reason)
- Admission for administration of anticancer therapy in the absence of any other SAEs (applies to oncology protocols)

Results in persistent or significant disability/incapacity

## Is a congenital anomaly/birth defect

Is an important medical event (defined as a medical event(s) that may not be immediately life-threatening or result in death or hospitalization but, based upon appropriate medical and scientific judgment, may jeopardize the participant or may require intervention [eg, medical, surgical] to prevent one of the other serious outcomes listed in the definition above.) Examples of such events include, but are not limited to, intensive treatment in an emergency room or at home for allergic bronchospasm; blood dyscrasias or convulsions that do not result in hospitalization.) Potential drug induced liver injury (DILI) is also considered an important medical event. (See Section 9.2.8 for the definition of potential DILI.)

Pregnancy and potential DILI must follow the same transmission timing and processes to BMS as used for SAEs (see Section 9.2.6 for reporting pregnancies).

Protocol Amendment No.: 05

Any component of a study endpoint that is considered related to study therapy should be reported as SAE (eg, death is an endpoint, if death occurred due to anaphylaxis, anaphylaxis must be reported).

#### **EVALUATING AES AND SAES**

## **Assessment of Causality**

- The investigator is obligated to assess the relationship between study intervention and each occurrence of each AE/SAE.
- A "reasonable possibility" of a relationship conveys that there are facts, evidence, and/or arguments to suggest a causal relationship, rather than a relationship cannot be ruled out.
- The investigator will use clinical judgment to determine the relationship.
- Alternative causes, such as underlying disease(s), concomitant therapy, and other risk factors, as well as the temporal relationship of the event to study intervention administration, will be considered and investigated.
- The investigator will also consult the Investigator's Brochure (IB) and/or Product Information for marketed products in his/her assessment.
- For each AE/SAE, the investigator must document in the medical notes that he/she has reviewed the AE/SAE and has provided an assessment of causality.
- There may be situations in which an SAE has occurred and the investigator has minimal information to include in the initial report to Sponsor. However, it is very important that the investigator always make an assessment of causality for every event before the initial transmission of the SAE data to Sponsor.
- The investigator may change his/her opinion of causality in light of follow-up information and send a SAE follow-up report with the updated causality assessment.
- The causality assessment is one of the criteria used when determining regulatory reporting requirements.

